Subjects will be hospitalized for a minimum of 8 days from start of the day 1 dose (ie, at least 72 hours after the day 5 dose) and for a minimum of 72 hours following day 12 and day 19 doses in cycle 1. If the subject receives a second cycle of AMG 673 at the same dose, hospitalization will be for a minimum of 8 days from start of the day 1 dose (ie, at least 72 hours after the day 5 doses). Hospitalization following day 12 and day 19 doses in cycle 2 and onwards will be at the discretion of the treating physician. For subjects receiving >2 cycles, hospitalization for cycle 3 onwards for all doses will be at the treating physician's discretion. However, in case of intra-subject dose escalation, subjects will be hospitalized as per the guidance for the first cycle. After re-start of treatment, after an interruption due to an adverse event(s), the subject will be hospitalized for a minimum of 48 hours. Subjects can be hospitalized for a longer time period at the discretion of the investigator.

For Schedule B, the drug will be administered as daily short term IV infusions for 14 days (cycle 1) and on D1, D4, D8 and D11 of each subsequent treatment cycle. There will be no infusion-free interval between cycle 1 and cycle 2, and the infusion-free interval after cycle 2 may range from 0-14 days based on safety data and anti-leukemia response to AMG 673 treatment and may be extended as described in [Section 6.2.1.1](#). The DLRT may make recommendation to alter dosing frequency starting from cycle 1 and beyond after evaluation of available PK, PD and safety data. Subjects will be hospitalized for a minimum of 15 days (ie, from day -1 through day 14 or the last dose of cycle 1). For cycle 2, subjects will be hospitalized for a minimum of 48 hours after each dose. For subjects receiving additional cycles (beyond cycle 2), hospitalization will be at the discretion of the treating physician. In case of intra-subject dose escalation, subjects will be hospitalized at least 48 hours after each dose increase. After an interruption due to an adverse event(s), the subject will be hospitalized for a minimum of 48 hours upon restart of treatment. Subjects can be hospitalized for a longer period at the discretion of the investigator.

Up to 12 total treatment cycles can be administered as long as in the judgment of the investigator the subject is deriving benefit.

Procedures:

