6.2.1.1.2 Schedule B

Schedule B will be initiated after preliminary safety data of AMG 673 in Schedule A (eg, MTD1 is estimated to be \geq 72 μ g) become available and may be conducted in parallel with Schedule A per sponsor's decision. For Schedule B, planned dose levels (dose per infusion) for the dose escalation cohorts are as follows: 72 μ g, 110 μ g, 160 μ g, 240 μ g, 360 μ g, 480 μ g and higher if MTD is not reached. The drug will be administered as short term IV infusions (approximately 30 minutes to 3 hours). The starting dose for the first

cohort on Schedule B will be 72 µg administered as short-term IV infusions daily (QD) during the 14-day cycle 1. No significant AMG 673 accumulation following QD dosing is predicted based on the preliminary PK analysis of Schedule A dosing. The doses administered for the cohorts following cohort 1 will include step-up doses administered in 2 day increments after the previous step-up dose (eg, cohort 2 will start with 72 µg for 2 days followed by 110 µg administered from day 3 to day 14; cohort 3 will start with 72 µg for 2 days followed by 110 µg from day 3 to day 4, followed by 160 µg from day 5 to day 14, etc). See [Table 3](#) below for more details.

Table 3. Schedule B - Cycle 1 Dosing

	D1 ^c	D2 ^c	D3	D4	D5	D6	D7	D8	D9	D10	D11	D12	D13	D14
Cohort 1	72 ^{ab}	72	72	72	72	72	72	72	72	72	72	72	72	72 ^b
Cohort 2	72 ^{ab}	72	110 ^{ab}	110	110	110	110	110	110	110	110	110	110	110 ^b
Cohort 3	72 ^{ab}	72	110 ^a	110	160 ^{ab}	160	160	160	160	160	160	160	160	160 ^b
Cohort 4	72 ^{ab}	72	110 ^a	110	160 ^a	160	240 ^{ab}	240	240	240	240	240	240	240 ^b
Cohort 5	72 ^{ab}	72	110 ^a	110	160 ^a	160	240 ^a	240	360 ^{ab}	360	360	360	360	360 ^b
Cohort 6	72 ^{ab}	72	110 ^a	110	160 ^a	160	240 ^a	240	360 ^a	360	480 ^{ab}	480	480	480 ^b

D = dose; Unit of dosage = µg

^a Dexamethasone 8 mg IV will be administered 1 hour prior to dose.

^b Additional PK samples will be taken at these time points as described in [Table 12-Table 14](#).

- [Table 13](#) PK sampling will be used only at the first dose of the target dose (highest dose planned) to be tested in Cycle 1 for each subject
- All subjects will undergo day 1 PK sampling as described in [Table 12](#).

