- PK sampling will occur on day 14-19 of Cycle 1 per [Table 12](#) if the subject will not receive cycle 2 immediately following cycle 1. If subject proceeds to Cycle 2, day 14 (post-dose) through day 19 samples will not be collected and Cycle 2 day 1 (eg day 15 after 1st dose) should be collected per [Table 14](#).

^c Upon recommendation of DLRT and Sponsor agreement, a lower starting dose may be used (eg, 36 µg) for up to the first 2 doses

The DLRT may recommend shortening the duration of steps to 1 day or to extend the duration of steps up to 5 days based on the emergent safety, PK and PD data. If the duration of step-up doses is extended, the duration of a cycle can be extended from 14 days to 28 days. All subjects will be pre-treated with an 8-mg dose of IV dexamethasone 1 hour prior to AMG 673 dose on day 1 and prior to each step-up dose of AMG 673.

Cycle 2 will consist of 4 AMG 673 infusions: day 1, day 4, day 8, and day 11 of a 14-day cycle at the target dose (maximum planned dose received from cycle 1) (see [Table 4](#) below). Cycle 1 schedule may be repeated 1 time before cycle 2 schedule is initiated upon agreement between the Investigator and Sponsor if the patient will likely

Approved

gain additional benefit per Investigator's assessment. If cycle 1 is not repeated, cycle 2 should begin immediately after cycle 1 with no dose free interval.

Table 4. Schedule B – Cycle 2 and Higher Dosing

	Day of Dose (14-Day Cycle)													
	1	2	3	4	5	6	7	8	9	10	11	12	13	14
Cohort 1	72 ^a			72				72			72			
Cohort 2	110 ^a			110				110			110			
Cohort 3	160 ^a			160				160			160			
Cohort 4	240 ^a			240				240			240			
Cohort 5	360 ^a			360				360			360			
Cohort 6	480 ^a			480				480			480			

Unit of dosage = µg

^a Dexamethasone 8 mg IV will be administered 1 hour prior to dose.

Upon recommendation from DLRT, the number of AMG 673 infusions in cycle 2 and higher may be adjusted based on emergent PK, safety, and PD data (eg, weekly [day 1 and day 8 of each cycle]). Subjects will be hospitalized for the whole duration of cycle 1 (ie, a minimum of 15 days), and for at least 48 hours after each AMG 673 administration in cycle 2 and higher. In the absence of any DLTs or SAEs, shorter hospitalization may be considered upon PI recommendation and Medical Monitor agreement after Cycle 2.

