6.2.1.4 Dosage Adjustments, Delays, Rules for Withholding or Restarting, Permanent Discontinuation

Treatment Interruption

Significant events requiring a change in treatment will be managed by immediate treatment interruption.

Note: The definition of treatment interruption may include interruption of infusion or delay of the subsequent infusion.

Events leading to treatment interruption may include:

- The subject experiences a clinically relevant grade 4 adverse event related or not-related to IP
- The subject experiences a grade ≥ 3 CRS
- Technical problem with the infusion pump / syringe pump
- The investigational product is incorrectly prepared or administered (eg, overdose)

Treatment Interruption and Re-Start in Case of Logistical Issues

If the infusion interruption or the delay of the next infusion was up to 3 days, the next dose can be administered as planned. If the infusion interruption or the delay of the next infusion was > 3 days, the instructions for re-start after interruptions due to adverse events described below should be followed.

Treatment Interruption and Re-Start in Case of Adverse Events

Specific instructions apply in case of CRS: In case of grade 2 or 3 CRS, treatment must be interrupted and delayed until the event resolves to CRS grade ≤ 1 . The Amgen medical monitor has to be consulted prior to a planned re-start. In case of grade 4 CRS, treatment must be permanently discontinued. See [section 6.6](#) for further details.

For all other adverse events, the following instructions apply:

Any clinically relevant (as determined by the investigator) grade 4 adverse event related to IP should lead to an interruption of treatment. Treatment should be interrupted until the event has resolved to grade ≤ 1 . Treatment may be resumed at the same dose or a lower dose after the event is resolved to grade ≤ 1 (see below for guidelines). Drug interruptions are also allowed in case of SAE not related to IP per investigator's discretion.

Approved

Re-start at a lower dose level:

In the following cases, the next infusion administered should be at the previous (lower) dose level:

- If the event occurred during the infusion and caused an interruption of the infusion of >72 hours, or
- if the event is defined as DLT and the subject has derived clinical benefit in the opinion of the PI after consultation with the Sponsor

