In both cases, re-escalation to the target dose can be considered for the next infusion if treatment at the lower dose has been well tolerated. An intermediate dose level may be administered prior to stepping up to the target dose after consultation with the Amgen medical monitor. After the dose step, assessments of vital signs, pulse oximetry and clinical evaluation should be performed as per the schedule of assessments for D1, D2 and D3 (Table 6 for Schedule A or Table 12 for Schedule B).

Re-start at the same dose can be performed if the infusion was interrupted for < 72 hours or if the event occurred after the end of the infusion and did not cause a delay of the start of the next infusion \geq 72 hours.

In case of re-appearance of the same grade 4 adverse event, IP should be permanently discontinued.

For persistent or re-occurring clinically relevant grade 3 adverse event related to IP, a dose reduction should be considered.

In any case, restarting treatment after an interruption due to an adverse event should be performed under medical supervision. The following assessments should be performed as described in the Schedule of Assessments (Table 6 for Schedule A or Table 12 for Schedule B) for D1, D2, and D3: vital signs, pulse oximetry, and clinical evaluation. The subject should be hospitalized for at least 72 hours after re-start of the infusion.

If possible, the number of infusions at the target dose in a cycle should sum up to the planned number of infusions (ie, 2 or 4 for Schedule A or a minimum of 70% of the planned target doses for Schedule B). In this case, the subject would still be DLT-evaluable. However, if the next infusion could only be administered with a delay of 5 days, a new cycle should be started and the interrupted cycle would not be evaluable for DLT.

Permanent Discontinuation

A subject will permanently discontinue treatment with investigational product in the event of:

- Dose-limiting or other unmanageable toxicity. Exception: If a DLT occurs in a subject with a clear clinical benefit from treatment a restart at the same dose level, a lower dose and / or implementation of a dose step can be considered if the toxicity has resolved and after consultation with the sponsor
 - Grade 4 CRS.
 - Grade 2 or 3 CRS meeting any of the criteria listed below:
 - Grade 2 or 3 CRS that does not improve to \leq grade 1 within 7 days.
 - Grade 3 CRS that does not improve to \leq grade 2 within 5 days.

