- The Amgen medical monitor must be consulted prior to re-starting treatment
- If CRS occurred during AMG 673 infusion, infusion has been interrupted for at least 72 hours
- The event has resolved to grade ≤ 1 prior to re-starting treatment

AMG 673 therapy should be restarted 1 dose level below the dose at which the event occurred. If this lower dose level is well tolerated (ie, absence of grade ≥ 3 CRS), then a dose step up to the subject's target dose level can occur. An intermediate dose may be administered after consultation with the Amgen medical monitor prior to stepping up to the target dose.

Please also refer to the general guidance for re-start of treatment after adverse events in [Section 6.2.1.4](#)

For Grade 3 and 4 CRS, please see [Section 2](#) for DLT considerations.

Tumor Lysis Syndrome

Subjects with AML and WBC $<10,000/\text{mcl}$ or $10 \text{ cells} \times 10^9/\text{L}$ are considered to be at low risk for tumor lysis syndrome. WBC $>10,000/\text{mcl}$ and $<50,000/\text{mcl}$ are considered to be at intermediate risk, and subjects with WBC $>50,000/\text{mcl}$ are considered at high risk. This protocol requires that subjects have a maximum WBC count of $15,000/\text{mcl}$ or $15 \text{ cells} \times 10^9/\text{L}$.

Additional high-risk features include baseline uric acid $>450 \text{ mcg/L}$ (7.5 mg/dl), serum creatinine $> 1.4 \text{ mg/dL}$, and lactate dehydrogenase (LDH) greater than the ULN.

Patients with intermediate risk WBC count and elevated baseline uric acid ($> 450 \text{ mcg/L}$), serum creatinine $>1.4 \text{ mg/dl}$, or LDH greater than ULN will be recommended to receive allopurinol prophylaxis. Typical dosing is 600-800 mg/day administered BID or QID and should begin 3 days before the first dose of study drug. Patients should be well hydrated and supplemented with intravenous fluid as clinically indicated.

For grade 3 and 4 tumor lysis syndrome, please see [Section 6.2.1.3](#) for DLT considerations.

Infection Prophylaxis

Subjects who may experience neutropenia for 7 days or longer are at a high risk for infectious complications. As appropriate, these subjects should be administered prophylactic antibacterial (eg, fluoroquinolones), antifungal and antiviral medications. These subjects should be monitored for early signs of breakthrough infections after the initiation of antibacterial therapy to prompt additional evaluation and possible therapy modification.

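### For Schedule B subjects in cohort 3 or higher interrupted mid-ramp, the re-start rules permit a step straight to the target dose (up to 6.67-fold), where Table 3 climbs one level at a time

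*Protocol*

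**What the plan says.** **Planned ramp.** Section 6.2.1.1.2 states: "The doses administered for the cohorts following cohort 1 will include step-up doses administered in 2 day increments after the previous step-up dose". Table 3 applies this to cohorts 2 to 6 on the ladder 72, 110, 160, 240, 360, 480 µg. Cohort 6 receives 110 µg on D3 and D4 and first reaches 480 µg on D11. Cycle 1 infusions are daily. Table 3's notes on PK sampling define the target through the "first dose of the target dose (highest dose planned) to be tested in Cycle 1 for each subject", so the target is the cohort's top dose and not the dose at which an event happened. Section 3.1 says that the Schedule B MTD is estimated using this step-up schedule.

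**Re-start after adverse events other than cytokine release syndrome (CRS), section 6.2.1.4.** This applies if the event occurred during the infusion and interrupted it for more than 72 hours, or if it was a DLT in a subject with clinical benefit. Then "the next infusion administered should be at the previous (lower) dose level". After that, "re-escalation to the target dose can be considered for the next infusion if treatment at the lower dose has been well tolerated". An intermediate level is optional, after consulting the medical monitor.

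**Re-start after grade 2 or 3 CRS, section 6.6.** The medical monitor must be consulted first and the event must have resolved to grade 1 or lower. Treatment resumes one level below the event dose. If that is tolerated, defined as no CRS of grade 3 or higher, a step to the subject's target may follow. "An intermediate dose may be administered after consultation with the Amgen medical monitor prior to stepping up to the target dose". No timing is given for the step.

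Neither rule is confined to Schedule A. Section 6.2.1.4 refers to Table 12 and to the 70% target-dose requirement, both of which belong to Schedule B. Neither section says whether the Table 3 ladder resumes after a re-start.

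**The concern.** The re-start rules suit a regimen with one step, where one level below the event dose and one step below the target are usually the same dose. Schedule B has up to five steps, so they can be far apart. A subject stopped at 110 µg in cohort 6 resumes at 72 µg. Four Table 3 levels (110, 160, 240 and 360 µg) then lie between the subject and the 480 µg target, and the re-start text permits all of them to be passed over.

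Two things are at stake:

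- **Safety.** The subjects for whom this route is open have just had CRS or another qualifying event. Section 6.6 itself warns that CRS can follow a dose step. The dose given next could depend on which section a site reads.
- **Estimation.** The Schedule B MTD is meant to describe the stepped regimen. The documents do not say how a DLT would be modelled if the subject reached target by another path.

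**Working it through.** The documents state no fold-increase on this point, so there is no figure of theirs to reproduce.

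**Inputs.** The ladder and the target of each cohort come from Table 3. The re-start dose (one level below the event dose) comes from sections 6.2.1.4 and 6.6, reading a level as a Table 3 level. The permitted next dose (the target) comes from the same two sections.

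**Planned steps** = next level / current level:

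- 110/72 = 1.53
- 160/110 = 1.45
- 240/160 = 1.50
- 360/240 = 1.50
- 480/360 = 1.33

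**Permitted jump** = target / level below the event dose:

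| Cohort (target, µg) | Event at 110 | Event at 160 | Event at 240 | Event at 360 | Event at 480 |
|---|---|---|---|---|---|
| 2 (110) | 110/72 = 1.53 | – | – | – | – |
| 3 (160) | 160/72 = 2.22 | 160/110 = 1.45 | – | – | – |
| 4 (240) | 240/72 = 3.33 | 240/110 = 2.18 | 240/160 = 1.50 | – | – |
| 5 (360) | 360/72 = 5.00 | 360/110 = 3.27 | 360/160 = 2.25 | 360/240 = 1.50 | – |
| 6 (480) | 480/72 = 6.67 | 480/110 = 4.36 | 480/160 = 3.00 | 480/240 = 2.00 | 480/360 = 1.33 |

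The last entry in each row is an event at the target itself. There the return is a single Table 3 step and nothing diverges. Cohort 2 has only that case. The other ten entries, in cohorts 3 to 6, exceed every step printed in Table 3.

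**Effect of the optional intermediate dose.** If one Table 3 level is inserted, the full ladder is restored in four of the ten cases: cohort 3 with an event at 110, cohort 4 at 160, cohort 5 at 240 and cohort 6 at 360. In the other six at least one level is still passed over. For the 72 to 480 µg case, the smaller of the possible largest steps is obtained with 160 as the intermediate: 160/72 = 2.22, then 480/160 = 3.00. This is arithmetic on the ladder and not a suggested sequence.

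**Table 3's own flexibility.** Footnote c allows a lower start, for example 36 µg, for up to the first two doses. If it replaces both, the planned D3 step is 110/36 = 3.06. The DLRT may also set step duration anywhere from 1 to 5 days. That changes how long a level lasts; it does not provide for omitting one.

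**Choice of top dose.** The dose lists in the synopsis and SAP section 3.1 stop at 360 µg and add that higher doses may follow. Sections 3.1 and 6.2.1.1.2 of the protocol and Table 3 name 480 µg. With a 360 µg target the maximum jump is 5.00.

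**The case against.** The strongest reply is that Table 3 is a plan and the re-start rules are an exception to it, hedged with safeguards. Much of that stands, and it rules out several stronger readings:

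- **A reader might infer that the two sets of rules cannot both be followed.** They can. The re-start text allows a return to target and does not order it, so resuming the ladder breaches neither section. For the same reason 480 µg is a permitted next dose in the example, not an instructed one.
- **A reader might infer a next-day jump to target after CRS.** The next-infusion wording is in section 6.2.1.4, under the instructions for adverse events other than CRS. Section 6.6 gives no timing, and refers to 6.2.1.4 only as general guidance.
- **A reader might take 6.67-fold as typical.** It needs cohort 6 and an event at 110 µg.
- **A reader might infer that such a DLT would enter the BLRM at the target dose.** No text says so. Appendix H groups subjects by dosing schedule, and the DLRT reviews drug administration. The documents are silent on this case.

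The safeguards are real. The lower dose must be well tolerated. Medical monitor consultation precedes a CRS re-start. CRS during an infusion requires at least 72 hours off drug. A 5-day delay starts a new cycle, and the interrupted one is not DLT-evaluable. Monitoring, hospitalization and dexamethasone accompany dose steps.

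What the reply does not supply is a stated Schedule B path for a subject stopped mid-ramp, or any limit on how many levels may be passed over.

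**Conclusion.** The point holds as a divergence between what the sections permit, not as a pair of incompatible instructions. It affects Schedule B subjects in cohort 3 or higher whose treatment is interrupted at an intermediate step before target. For them the largest permitted jump is 2.22-fold (cohort 3), 3.33 (cohort 4), 5.00 (cohort 5) and 6.67 (cohort 6), each for an event at 110 µg. The comparators are 1.33 to 1.53 for the printed steps, or 3.06 on D3 under footnote c. Subjects whose event occurs at the target are not affected.

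The figures assume the Table 3 ladder, no intermediate dose, and a 480 µg top level. The consequence for MTD estimation is an inference from silence and is not quantified. The point is more than missing detail, because a stated rule, applied as written, allows a much larger increase after CRS than the planned ramp contains.

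**What to change.** Reconcile sections 6.2.1.4 and 6.6 with section 6.2.1.1.2 and Table 3 for Schedule B, so that one return path applies to a subject interrupted mid-ramp. State whether Table 3 levels may be bypassed and, if so, on whose decision. Give the timing in both re-start sections or say that it is left open. The path is for the clinical team to decide, and none is proposed here.

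On the statistical side, flag in the DLRT listing and the BLRM data every subject whose path to target departed from Table 3, and say how a DLT in such a subject is to be handled.

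The cost is protocol wording in two sections, one flag, and a sentence on the model data. No new data collection is needed, since doses and infusion times are already recorded on the eCRF.
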